#### 1.1.3 Research Basis

ARDS is often complicated with RVD, and the incidence can be as high as 64%. ARDS patients with RVD have a worse prognosis and a significantly higher risk of death, which is an independent risk factor for death in ARDS patients. Randomized controlled studies have shown that compared with low tidal volume ventilation, APRV can increase average airway pressure [7], which may theoretically increase intrathoracic pressure and extrapericardial pressure, thereby affecting venous return, increasing pulmonary circulation resistance, leading to right heart dysfunction and even hemodynamic deterioration. However, the actual effect of APRV on right heart function in ARDS patients has not been reported.

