#### 2. Study Objective/end point

**Objective**: To study the effect of APRV on right ventricular function in ARDS patients.

**Primary endpoint/outcome**: Effect of APRV mechanical ventilation for 24 hours on right heart function in ARDS patients.

**Secondary end point/outcome**: Effects of APRV ventilation at 6h, 12h, 48h, 72h and 24h after APRV ventilation on right heart function in ARDS patients.

Effects of APRV ventilation at 6h, 12h, 24h, 48h, 72h and 24h after APRV ventilation on hemodynamics of ARDS patients.

Mortality rate of ARDS patients on APRV mechanical ventilation at 28 days after enrollment, length of stay in ICU, length of stay, and mortality rate in hospital.

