# 3.3 Sample size

This study is to study the effect of APRV on right heart function. Referring to previous literatures, the number of subjects is generally required to be 40, and the number of subjects should be increased to 50 in consideration of shedding and withdrawal, etc.

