#### 8. Statistical analysis and statistical methods

Prism 4.01 was used for statistical analysis software.Because all the parameters are non-normally distributed, the data is represented as the median (quartile range;Head).Friedman ANOVA of repeated measurements was used to compare the data obtained at each step and, where appropriate, through Dunn post hoc tests using Bonferroni correction.Qualitative data were compared with Fisher's exact test.All comparisons were double-tailed, with P<0.05 indicating the existence of significant differences.

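### Section 8 judges the primary 24 h effect by P<0.05 alone, with no paired change and confidence interval, so P≥0.05 could not separate no change from too little information

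*Protocol*

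**What the plan says.** Section 2 gives the primary endpoint as "Effect of APRV mechanical ventilation for 24 hours on right heart function in ARDS patients". It names no measured variable and no size of change.

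Section 8 sets the inference. "Friedman ANOVA of repeated measurements was used to compare the data obtained at each step", followed where appropriate "through Dunn post hoc tests using Bonferroni correction". "All comparisons were double-tailed", with "P<0.05 indicating the existence of significant differences". Results are summarised by medians and quartiles. The number of comparisons covered by the Bonferroni correction is not given.

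On sample size, section 3.3 says "Referring to previous literatures, the number of subjects is generally required to be 40", raised to 50 for losses.

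The reason for the study is in section 1.1.3: APRV may in theory raise intrathoracic pressure and pulmonary resistance, "leading to right heart dysfunction and even hemodynamic deterioration".

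**The concern.** The protocol wants to know whether, and by how much, right heart function changes after 24 hours of APRV, and its background raises possible deterioration. A threshold on P says at most that some difference exists. It does not say how large the change is or which changes the data rule out.

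This matters most when P≥0.05. To interpret such a result, a reader needs either an interval for the change or a sample size tied to a stated detectable change. The protocol gives neither. Separate medians at each time do not fill the gap, because the difference between two medians is not the median within-patient change and comes with no measure of its uncertainty.

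The planned test also spreads the error rate over many time points, although section 2 singles out one. The primary contrast therefore carries a multiplicity penalty that the choice of endpoint does not require.

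**Working it through.** **Inputs from the protocol.** Two-sided 0.05 and Friedman with Dunn-Bonferroni (section 8). Seven scans: before APRV, at 6, 12, 24, 48 and 72 h, and 24 h after APRV (section 5). 40 patients, raised to 50 (section 3.3).

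**Assumptions, because the protocol gives no figure.** All 40 patients have all seven scans; normal errors; equal within-patient correlation of 0.5; a shift present at all on-APRV scans; Bonferroni over either the 6 contrasts with baseline or all 7×6/2 = 21 pairs. The SD of a change is SD×√(2(1−ρ)), which at ρ = 0.5 equals the SD of a single measurement.

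**The plan's own figure.** The 40 cannot be reproduced, as no effect size, SD or power is stated. The step to 50 fits a 20% loss: 40/(1−0.20) = 50. The rate itself is not stated.

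**The hurdle set by Dunn-Bonferroni.** Two time points differ if their rank sums differ by more than z×√(nk(k+1)/6). With n = 40 and k = 7, √(40×7×8/6) = 19.32.
- 21 pairs: z = 3.04, threshold 58.7, a mean rank difference of 58.7/40 = 1.47.
- 6 contrasts: z = 2.64, threshold 51.0, a mean rank difference of 51.0/40 = 1.27.

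**Power for 24 h against baseline.** The planned rule was simulated (Friedman P<0.05 and Dunn significant; 2000 to 4000 runs per setting; repeat runs agree within a few points). The last column is one uncorrected paired test: simulated Wilcoxon at 0.4 and 0.5 SD, and Φ(d√40 − 1.96) at 0.6 and 0.8 SD.

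| True change | Planned rule, 21 pairs | Planned rule, 6 contrasts | One paired test |
|---|---|---|---|
| 0.4 SD | about 20% | about 34% | about 67% |
| 0.5 SD | about 37% | about 57% | about 85% |
| 0.6 SD | about 60% | about 77% | about 97% |
| 0.8 SD | about 90% | about 96% | >99% |

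**Sensitivity.**
- With correlation 0.7, a change of 0.5 SD of a single measurement is 0.5/√0.6 = 0.65 SD of the change, and the planned rule reaches 71 to 84%.
- With only 30 patients complete at all seven scans, as the standard Friedman test requires, 0.5 SD at correlation 0.5 gives about 25% over 21 pairs and 35 to 38% over 6.

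**Precision of the alternative.** The 95% half-width for a mean paired change is t(0.975, 39)/√40 = 0.320 SD of the change. A simulated Hodges-Lehmann interval gives about 0.32. With 50 pairs the half-width is about 0.28.

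**Detectable change at 80% power, 40 pairs, paired t-test.** 0.454 SD at two-sided 0.05, but 0.652 SD at 0.05/21. The first figure applies only if the 24 h contrast is tested alone.

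**The case against.** Several points on the other side are sound.

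- **Later documents.** The choice of estimator and interval often sits in a statistical analysis plan. Section 10.5.1 mentions a statistical analysis proposal, and section 8 does not exclude intervals. This lowers the weight of the omission but does not remove it: section 8 already fixes summary, tests, correction and criterion, and that stated rule suits the primary question poorly. The basis for the sample size is protocol content in any case.
- **Summaries are planned.** It would be too broad to say that the plan has no estimates, since medians with quartiles give a view of each time point. What is missing is the paired change with its interval.
- **Power depends on assumptions.** A reader might infer that a relevant deterioration will probably be missed. The documents do not support that. They define no relevant change and no Bonferroni family, and the direction reverses with 6 contrasts instead of 21 at 0.5 SD, with an effect of 0.6 SD or more, or with correlation 0.7.
- **No misreading is written down.** A reader might also infer that P≥0.05 will be reported as APRV leaving the right heart unaffected. No section says so. The protocol only lacks anything to prevent it.
- **The objective is neutral.** Section 2 asks about an effect, section 8 is two-sided, and the harm mechanism in section 1.1.3 is offered as theory. A compulsory no-harm margin would redesign the study and is not needed to repair the analysis.

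**Conclusion.** The point holds in a limited form and should be acted on. As written, the only criterion for the primary 24 h effect is P<0.05 from a multiplicity-corrected comparison across all time points, with no paired change and no interval. Because section 3.3 links 40 patients to no effect size, SD or power, P≥0.05 could not distinguish no change from not enough information.

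The loss against a direct paired test is largest for moderate changes. Under the assumptions above it is about 67 − 34 = 33 to 67 − 20 = 47 percentage points at 0.4 SD, and 85 − 57 = 28 to 85 − 37 = 48 at 0.5 SD. It is under 10 points at 0.8 SD. The data remain usable throughout; what suffers is the answer that can be drawn from them.

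**What to change.** **Section 8.** Name one right heart variable as primary. Make its 24 h minus pre-APRV paired change the primary result, reported as a Hodges-Lehmann estimate with 95% confidence interval. Keep Friedman with Dunn-Bonferroni for the other time points and state how many comparisons the correction covers. Add that P≥0.05 is not evidence of no effect. A limit for concluding no harm, set in advance, is optional.

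**Section 3.3.** State the precision that 40 pairs are expected to give: a 95% half-width of about 0.32 SD of the change. Quote 80% power for about 0.45 SD only if the 24 h contrast is tested alone at two-sided 0.05; beside a Bonferroni-corrected test it would overstate the power.

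**Cost.** One extra analysis and a few sentences. No extra patients or measurements. The paired change needs only the pre-APRV and 24 h scans, so it also keeps patients who miss a later scan.

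**Gain.** Whatever the P value, the result would show which sizes of change the data are compatible with.

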#### 9.Medical treatment and protection of subjects

#### 9.1 Risk assessment of subjects and risk disposal measures and plans

(1) Reporting method: Any adverse events, such as subjects' subjective

discomfort and abnormal laboratory testing, should be treated seriously and analyzed carefully, and immediate measures should be taken to protect the safety of subjects.

(2) Processing procedures: record in detail, and retest according to the situation, record its persistence, return, disappearance and other conditions.

(3) Follow-up of unalleviated adverse events. All adverse events should be followed up until they are properly resolved or the condition is stable.

# 9.2 Medical treatment and protection of subjects during the study

The rights and welfare of the subjects will be protected during the study, and the quality of their medical care will not be affected by their refusal to participate or withdrawal from the study.

If the patient drops out of the study, we will no longer conduct study related tests.

The investigator will provide insurance for the subjects participating in the study program. If the subjects suffer any damage related to the study, they will receive timely and free treatment and be compensated or compensated according to laws and regulations and mutual agreements.

# 9.3 Medical treatment and protection of subjects after study

APRV was administered in a study manner during the study, with inclusion/exclusion criteria clearly defined, and efficacy and safety information recorded.Routine treatment was continued after the study.Subjects shall not be required to waive their right to free treatment and compensation for study related damages.

## **10.Supporting documents and notes**

#### **10.1 Informed consent process**

Informed consent was completed before the subjects' relatives agreed to participate in the study and continued throughout the study. Informed consent was approved by the ETHICS committee, and the relatives of the study subjects should read the informed consent.Researchers explain the process and answer questions

from relatives. The subjects were also informed of possible risks to their relatives and their rights.

Relatives of the study subjects may discuss it with other family members or guardians before agreeing to participate. The investigator must inform relatives that study participation is voluntary and that they may withdraw from the study at any time during the study. Copies of the informed consent can be provided to the relatives of the subjects for preservation. The rights and welfare of relatives of the study subjects will be protected and it is stressed that the quality of their medical care will not be affected by their refusal to participate in the study.

# **10.2 Privacy protection**

Research object information kept by member of project quality control, by the relevant forms, records and samples for storage, without violating confidentiality and related laws and regulations, arbitrator, ethics committee and the pharmaceutical supervisory and administrative department inspectors can check original medical records, in not approved consent before any research information cannot be disclosed to unauthorized third party.

# 10.3 Collection and use of specimens and data

Blood samples collected by the institute are only used for routine medical tests during treatment, so no residual specimens will be retained.

After the study, the retained image data and other data will be used for future research with the consent of the subjects.

# 10.4 Quality control and quality assurance

All physicians participating in this study were required to familiarize themselves with the APRV mechanical ventilation pattern and the use of bedside ultrasound.All physicians participating in this study should master respiratory mechanics measurement methods.

The CRF form should be checked by two persons.

The project quality control leader shall conduct quality control on the study

data every week to ensure the safety, accuracy and order of the test.

# 10.5 Data processing and record keeping

#### 10.5.1 Data collection and management

The required data were collected from medical records of patients who met the inclusion criteria and filled in paper case reports(CRF).

Data collection will be carried out by clinical researchers under the supervision of the director, who will be responsible for the accuracy, completeness and timeliness of the reported data.All data shall be clear to ensure accurate interpretation and traceability.

Data entry: Remote data entry shall be carried out after the training of data entry staff, which shall be completed by two persons independently by using the double-copy entry method.

Data review: Manual comparison of data in the case report form and the database to ensure that the data in the database are consistent with the results in the case report form.

Data locking: In addition to the above data review, the principal investigator, statistician, data manager and sponsor representative shall further discuss and confirm the main content of the study proposal and the statistical analysis proposal.Conduct audit to confirm that all data have been entered into the database, all questions have been resolved, and the analysis group has been defined and judged before locking the data.

Clinical data will be stored in a database, which shall be password protected and logical proofreading procedures shall be set up when the database is established.

#### 10.5.2 Research data retention

The minimum retention time of all data and original documents should be 1 year and permission should be obtained before destruction.

# 10.6 Declaration of conflict of interest

There is no conflict of interest between this study and any physician

participating in this clinical study
